Pharmacokinetic: A linear fixed effect model with treatment as a fixed effect will be fitted to the log-transformed PK parameters AUC(INF), Cmax, AUC(0-T) for use in estimation of effects and construction of CIs. To assess comparability of Process E belatacept to Process C belatacept, point estimates and the 2-sided 90% CIs for treatment differences on the log scale will be exponentiated to obtain estimates for ratios of geometric means and respective 90% CIs for belatacept AUC(INF), Cmax, and AUC(0-T) on the original scale. A sensitivity analysis comparing the PK between Process E and Process C may be performed by excluding patients who are positive for anti-belatacept antibodies. Biocomparability of Process E belatacept to Process C belatacept will be concluded if the 90% CIs for the ratios of geometric means for belatacept AUC(INF) and Cmax are contained within 80% to 125%.

All individual PK parameters will be listed for each analyte, including exclusions and reasons for exclusion from summaries. Summary statistics will be provided for each PK parameter by treatment, for belatacept. Geometric means and coefficients of variation will be presented for Cmax, AUC(0-T), AUC(INF), CLT, and Vss by treatment group. Medians and ranges will be presented for Tmax by treatment group. Mean and standard deviation will be provided by treatment group for T-HALF.

Plots of individual AUC(INF), Cmax, and AUC(0-T) combined with corresponding geometric means will be provided versus treatment.

Immunogenicity: The incidence of positive response will be summarized in a table by study day and the corresponding titer values will be listed. The impact of anti-belatacept on PK parameters will also be evaluated in individual subjects.

Safety: All recorded AEs will be listed and tabulated by system organ class, preferred term, and treatment. Vital signs and clinical laboratory test results will be listed and summarized by treatment. Any significant physical

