4.4 Method of Assigning Subject Identification

Enrolled subjects, including those not dosed, will be assigned sequential subject numbers starting with 00001, (eg, 00001, 00002, 00003.... 00010). Those enrolled subjects meeting inclusion and exclusion criteria will be eligible to be randomized. Randomization numbers will be assigned prior to dosing.

Previous studies indicate that in subjects who take belatacept, there is a trend in higher clearance with increasing body weight.⁴ In this study, the randomization will be stratified by weight categories: 60 to < 70 kg, 70 to < 80 kg, 80 to < 90 kg, and 90 to 100 kg. Within each weight category, subjects will be randomly assigned to Process E belatacept or Process C belatacept in 1:1 ratio. Randomization numbers will be sequential within each weight category, starting with 1001, 2001, 3001, and 4001 for each weight category, respectively.

Subjects will not be replaced if they are discontinued from the study secondary to an AE unless the AE can be determined to be unrelated to treatment. If a subject is replaced after dosing then the replacement subject will be assigned the original subject's number plus 500. The replacement subject will receive the same treatment as the subject being replaced but a new randomization number will be assigned to him or her. For example, Subject 4 would be replaced by Subject 504.

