8.4.4 Pharmacokinetic Analyses

A linear fixed effect model with treatment as a fixed effect will be fitted to the log-transformed PK parameters AUC(INF), Cmax, AUC(0-T) for use in estimation of effects and construction of CIs. To assess comparability of Process E belatacept to Process C belatacept, point estimates and the 2-sided 90% CIs for treatment differences on the log scale will be exponentiated to obtain estimates for ratios of geometric means and respective 90% CIs for belatacept AUC(INF), Cmax, and AUC(0-T) on the original scale. A sensitivity analysis comparing the PK between Process E and Process C may be performed by excluding patients who are positive for anti-belatacept antibodies. Biocomparability of Process E belatacept to Process C belatacept will be concluded if the 90% CIs for the ratios of geometric means for belatacept AUC(INF) and Cmax are contained within 80% to 125%.

All individual PK parameters will be listed for each analyte, including exclusions and reasons for exclusion from summaries. Summary statistics will be provided for each PK parameter by treatment, for belatacept. Geometric means and coefficients of variation will be presented for Cmax, AUC(0-T), AUC(INF), CLT, and Vss by treatment group. Medians and ranges will be presented for Tmax by treatment group. Mean and standard deviation will be provided by treatment group for T-HALF.

Plots of individual AUC(INF), Cmax, and AUC(0-T) combined with corresponding geometric means will be provided versus treatment.

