1 BACKGROUND AND RATIONALE

Background:

Renal transplantation is the most effective treatment for adults and pediatric patients of all ages with end stage renal disease. Compared with dialysis, kidney transplantation offers improved medical outcome, cognitive function, social adjustment, and quality of life.^{1,2} Significant unmet medical needs remain in kidney transplantation, among which is the need for new therapies that can reduce the substantial toxicities associated with calcineurin inhibitor-based immunosuppressive regimens.

Study Rationale:

This will be an open-label, randomized, parallel-group, single-dose study to compare the PK of belatacept between 2 drug products manufactured by 2 different processes administered in healthy subjects. Parallel design was selected because the long half-life (T-HALF; approximately 10 days) would make it operationally challenging to washout and retain subjects, and the potential impact of immunogenicity response on PK in a crossover design. Previous studies have shown that there is a trend of higher clearance with increasing body weight.⁴ Belatacept has linear PK from 1 to 20 mg/kg. This study will assess the most clinically applicable dose, 10 mg/kg, which is the highest approved dose. Belatacept has been given as single doses to normal healthy volunteers (NHVs) and shown to be safe and well tolerated.⁵ There have been no deaths or serious adverse events (SAEs), and no subjects have discontinued from a study due to adverse events (AEs) in the pooled NHV population. A study in healthy volunteers is considered to be more sensitive in evaluating the product similarity because it is likely to produce less PK

variability compared with that in patients with potentially confounding factors such as underlying and/or concomitant disease and concomitant medications.⁶

Research Hypothesis:

The PK of belatacept manufactured by Process E (Process E belatacept) and by Process C (Process C belatacept) are comparable in healthy subjects, based on exposure as measured by area under the serum concentration-time curve (AUC) from time zero extrapolated to infinite time (AUC[INF]) and maximum observed serum concentration (C_{max}).

Schedule of Analyses:

Final analysis will be performed following database lock according to agreed-upon reporting milestone(s), typically after all subjects have completed the study.

Exclusions of Site 2 Data Due to Major Protocol Deviations:

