Prior to protocol amendment 02 (dated September 27, 2016), 146 subjects were dosed at 3 clinic sites: 60 at Site 1 (PPD), 30 at Site 2 (SNBL), and 56 at Site 3 (MRA). Audit and monitoring visits revealed major protocol deviations at Site 2 including but not limited to inclusion/exclusion criteria deviations, not providing HIPAA consent at screening visit, incomplete source documentation, failure to obtain laboratory tests within the pre-specified windows, failure to obtain protocol-specified laboratory tests, and incorrect handling of blood samples. Due to the number and significance of these deviations affecting the data of all subjects at Site 2, the 30 dosed subjects were not considered eligible for the analysis of the study endpoints.

Removing the data from the 30 dosed subjects at Site 2 from the analysis without replacing it would result in a total of 116 dosed subjects and under-power the study (approximately 74% power, assuming a true difference of 11%).

The protocol amendment 02 (dated September 27, 2016) was written to replace those 30 dosed subjects at Site 2 with 30 new subjects at Site 1 and Site 3, in order to maintain sufficient power. Randomization of the 30 new subjects was stratified by weight categories in the same way as for the originally planned subjects.

The 30 dosed subjects at Site 2 will not be included in the analysis and 30 replacement subjects dosed at Site 1 and Site 3 will be included in the analysis. A total of 176 subjects will be dosed including the originally planned 146 subjects and the 30 replacement subjects.

In addition, the data from the subjects who were enrolled at Site 2 will only be presented in the listings and be excluded from any summaries or statistical analyses.

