2.2 Treatment Assignment

Subjects will be randomly assigned to Process E belatacept or Process C belatacept in 1:1 ratio according to a computer-generated randomization scheme, stratified by weight categories: 60 to < 70 kg, 70 to < 80 kg, 80 to < 90 kg, and 90 to 100 kg. Randomization numbers will be assigned prior to dosing.

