7.1 General Methods

The data from the subjects who were enrolled at Site 2 will not be included in any summaries or statistical analyses. These data will only be presented in the listings. Details of the data presentation are specified in the DPP. The data from the 30 replacement subjects along with the data from the initial 116 subjects who were enrolled and dosed at the other sites will be used for analyses.

All data recorded on case report forms will be listed by subject. Descriptive summaries will be presented for continuous variables using number of subjects (N), mean, standard deviation (SD), median, minimum and maximum. Geometric mean and coefficient of variation (CV%) will also be presented for sample serum concentration-time data and PK parameters. Descriptive summaries for categorical variables will utilize counts and percentages.

For all treatment comparisons, a linear fixed effect model with treatment as a fixed effect will be fitted to the log-transformed PK parameters C_{max}, AUC(0-T) and AUC(INF) for use in estimation of effects and construction of CIs. Point estimates and 90% CIs for differences on the log-scale will be exponentiated to obtain estimates for ratios of geometric means and respective 90% confidence intervals on the original scale. The SAS procedure (PROC MIXED) will be used to derive all inter-subject variances, and for the estimation of test to reference ratios and respective confidence intervals.

Adverse events and medical history will be coded according to the most recent Medical Dictionary for Regulatory Activities (MedDRA) version. Previous and concomitant medications will be coded using the BMS Drug Dictionary.

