7.7 Pharmacokinetics

The PK population will be used for all listings. Evaluable PK population will be used for summary statistics and statistical analyses. Analysis will include all analyte data in the PK dataset for belatacept.

Subject serum concentration-time data will be listed and summarized by treatment and nominal collection time for belatacept. Details of T-HALF derivation and the harmonic mean of terminal slope by treatment will also be presented. Plots of individual serum concentration profiles over time will be provided. Overlay of individual serum concentration profiles over time will be provided by treatment. Plots of mean (+SD) serum concentration profiles versus time will be presented for belatacept, and both treatments will be superimposed on the same plot.

All individual PK parameters will be listed for belatacept including any exclusions and reasons for exclusion from summaries. Summary statistics will be tabulated for each PK parameter by treatment. Geometric means and CV% will be presented for Cmax, AUC(0-T), AUC(INF), CLT, and Vss. Medians and ranges will be presented for Tmax. Arithmetic mean and standard deviation will be presented for T-HALF. Decimal place specifications for summary statistics are described in Section 7.10.

Separately by antibody status (negative antibody status with respect to baseline as defined in Section 7.9) and overall, a linear fixed effect model with treatment as a fixed effect will be employed. Kenward-Rogers degrees of freedom will be specified in the model. Point estimates and 90% CIs for treatment differences on the log-scale will be exponentiated to obtain point estimates and 90% CIs for the ratios of geometric means on the original scale. A sensitivity analysis comparing the PK between Process E and Process C may be performed by excluding patients who are positive for anti-belatacept antibodies. The following SAS code will be implemented, where A is the Process E belatacept, and B is the Process C belatacept.

Plots of individual Cmax, AUC(0-T) and AUC(INF) combined with corresponding geometric means will be provided versus treatment.

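### Randomisation is stratified by four weight categories, but the primary equivalence model contains treatment only; adding the stratum costs almost nothing and may narrow the 90% CIs

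*Protocol*

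**What the plan says.** Protocol 4.4 states: "In this study, the randomization will be stratified by weight categories". SAP 2.2 confirms that the scheme is "stratified by weight categories: 60 to < 70 kg, 70 to < 80 kg, 80 to < 90 kg, and 90 to 100 kg", with 1:1 allocation. The reason is given in Protocol 4.4 and in SAP Section 1, where previous studies are said to show that "there is a trend of higher clearance with increasing body weight". For the subjects added after the Site 2 exclusion, SAP Section 1 says: "Randomization of the 30 new subjects was stratified by weight categories in the same way as for the originally planned subjects".

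The analysis model is described in four places, and treatment is the only effect named in any of them:

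- Protocol 8.4.4, and in the same words the Protocol Synopsis (Analyses, Pharmacokinetic): "A linear fixed effect model with treatment as a fixed effect will be fitted to the log-transformed PK parameters AUC(INF), Cmax, AUC(0-T".
- SAP 7.1: "a linear fixed effect model with treatment as a fixed effect will be fitted to the log-transformed PK parameters".
- SAP 7.7: "a linear fixed effect model with treatment as a fixed effect will be employed".

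The only sensitivity analysis named for the treatment comparison concerns anti-belatacept antibody status. Biocomparability is concluded if the 90% CIs for the AUC(INF) and Cmax ratios both lie within 80% to 125%.

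**The concern.** Stratifying by weight removes between-stratum variation from the true error of the treatment difference. A model without the stratum leaves that variation in the residual, so the standard error it reports is too large whenever weight explains some exposure variance. The CIs that decide the trial would then be wider than the design requires.

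Power matters here: SAP Section 1 justifies dosing 30 more healthy subjects by the power that would otherwise be lost.

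There is also a secondary reason to adjust. Balance by weight is less certain in the analysis set than at randomisation. Thirty Site 2 subjects are removed, 30 are added at Sites 1 and 3, and only subjects with adequate PK profiles are analysed. The two documents also differ on allocation of replacements: Protocol 4.4 gives a replacement the treatment of the subject replaced, while SAP Section 1 describes new stratified randomisation. A treatment-only model carries any resulting weight imbalance into the estimated ratio.

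**Working it through.** **Inputs.** From the Protocol Synopsis (Sample Size): 67 evaluable subjects per arm, CVs of 20% (AUC(INF)) and 26% (Cmax), true ratio 0.90 or 1.11, limits 0.80 to 1.25, 90% CIs. From Protocol 4.4: four strata, 1:1 within each. The share of log-exposure variance explained by the strata, R², is not given, so I assume 0, 5, 10 and 20%.

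**1. Reproduce the stated power.** The log-scale SD is σ = √ln(1+CV²), which gives 0.198 and 0.256. The standard error is σ√(2/67), or 0.0342 and 0.0442. With t(0.95; 132 df) = 1.656, the CI half-widths are 0.057 and 0.073. Power of the two one-sided tests, integrated over the chi-square distribution of the residual variance, is 96.2% for AUC and 84.3% for Cmax at a ratio of 0.90. Their product is 81.1% (endpoints treated as independent). At 1.11 the figures are 96.5, 84.8 and 81.8%. The stated 96/84/81% is reproduced. It uses total CVs, so it claims no gain from weight.

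**2. Effect of leaving out the stratum.** With balance within strata, the true variance of the difference is (1−R²)·2σ²/67, while the treatment-only model estimates 2σ²/67.

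- Coverage of the nominal 90% CI is 2F(1.656/√(1−R²)) − 1, with F the t distribution on 132 df. The one-sided error is 1 − F(1.656/√(1−R²)).
- The adjusted model uses (1−R²) throughout and 129 df. Its CI width relative to plan is (1.6568/1.6565)·√(1−R²).

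Results with the same R² on both endpoints and a true ratio of 0.90 (gains taken from unrounded powers):

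| Assumed R² | Adjusted CI width vs plan | Unadjusted coverage | Unadjusted one-sided error | Joint power, treatment only | Joint power, with stratum | Gain (points) |
|---|---|---|---|---|---|---|
| 0 | 1.0002 | 90.0% | 5.0% | 81.1% | 81.1% | 0.0 |
| 5% | 0.975 | 90.8% | 4.6% | 82.0% | 83.2% | 1.2 |
| 10% | 0.949 | 91.7% | 4.2% | 83.0% | 85.3% | 2.4 |
| 20% | 0.895 | 93.4% | 3.3% | 84.9% | 89.3% | 4.4 |

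The treatment-only column also rises with R², because the stratified design helps even an unadjusted analysis. With 73 per arm the gains are 1.0, 2.0 and 3.7 points.

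**3. Weight affects AUC only.** With R² of 5, 10 and 20% on AUC and none on Cmax, the joint gain is 0.3, 0.5 and 0.8 points, because Cmax limits joint power.

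**4. What R² might look like.** Suppose exposure after mg/kg dosing is proportional to weight^b, which for AUC means clearance proportional to weight^(1−b), and weights are uniform on 60–100 kg. The variance of log weight is then 0.0215, of which 0.0201 lies between strata, so R² = b²·0.0201/σ².

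| b | R², AUC | R², Cmax | Joint gain (points) |
|---|---|---|---|
| 0.10 | 0.5% | 0.3% | 0.1 |
| 0.25 | 3.2% | 1.9% | 0.5 |
| 0.50 | 12.8% | 7.7% | 2.0 |
| 0.75 | 28.8% | 17.3% | 4.1 |

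At b = 0 (clearance proportional to weight) there is nothing to gain.

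**5. Simulation check.** I used 134 subjects, permuted blocks of 4 within four strata (block size assumed) and 15,000 trials per setting. The joint gains were 1.2, 2.2 and 4.5 points at R² of 5, 10 and 20%. At a true Cmax ratio of 0.80, false equivalence was 4.2% unadjusted against 5.0% adjusted (R² 10%), and 3.2% against 4.9% (R² 20%).

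**6. Weight imbalance.** If mean weights were 81 and 79 kg (assumed), the unadjusted ratio shifts by a factor (81/79)^b. That is about 0.3, 0.6, 1.3 and 1.9% for the four values of b.

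**The case against.** The strongest reply is that nothing in the plan is wrong. The test is valid, false equivalence is not inflated, and the sample size was set on total CVs, so the promised power is met without adjustment. That stands: this is a point about efficiency.

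The benefit also rests on an unreported R². The documents give only a qualitative trend in clearance, dosing is already per kg, and no weight effect on Cmax is reported. This stands too, and it is why the gain is given as a range that includes zero.

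The SAS code announced in SAP 7.7 is missing from the public text, and SAP 7.10.1 refers to an adjusted geometric mean, so a stratum term in the code cannot be ruled out. But the model is written four times with treatment alone. If the code differs, the text needs correcting anyway.

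The 2 kg imbalance is on the large side. In a simulation of the removal and replacement of 30 subjects with new stratified allocation, the SD of the mean weight difference was about 1.1 kg, and 2 kg or more occurred in about 8% of trials. A 1.1 kg difference at b = 0.25 moves the ratio by about 0.35%, small against half-widths of about 5.7% and 7.3%. Imbalance is therefore only a supporting reason.

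Finally, changing the primary model of an open-label trial after dosing in order to narrow the deciding CIs invites questions. That calls for a documented reason and a change before database lock. It does not defeat the change, because the reason comes from the design and not from the data.

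**Conclusion.** The concern holds. The plan stratifies on weight and then leaves weight out of the primary model without explanation. The result is a valid but possibly conservative analysis. With R² of 5 to 20% on both endpoints, the CIs could be 2.5 to 10.5% narrower and joint power 1.2 to 4.4 points higher at a true ratio of 0.90. The gain is below 1 point if only AUC depends on weight, and nil if neither endpoint does. These figures assume 67 per arm, the stated CVs, balance within strata and independent endpoints. If balance within strata is lost, the unadjusted coverage moves back towards 90%. The change should be made because its downside is negligible, not because the planned conclusion would be unsound.

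**What to change.** Before database lock, add the randomisation weight stratum (four levels) as a fixed effect to the primary model in the Protocol Synopsis, Protocol 8.4.4, and SAP 7.1 and 7.7. Base the primary 90% CIs on the adjusted treatment difference, and keep the treatment-only model as a supportive analysis. State that the reason is the stratified randomisation, since the study is open-label and subjects have already been dosed. Check that the SAS code matches the text, and reconcile Protocol 4.4 with SAP Section 1 on how the replacement subjects were allocated.

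The cost is one term in PROC MIXED and 3 of 132 residual degrees of freedom. If weight has no effect and the strata are balanced, the CI widens by about 0.02% (0.05% in simulation). With some loss of within-stratum balance, taken as 1% variance inflation, it would widen by about 0.5%, and an R² of about 1% would recover that. No new data are needed, but both documents need a documented amendment.

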Study Population: Healthy male and female subjects, including women of childbearing potential, ages 18 to 55 years inclusive, as determined by medical history, physical examination, vital signs, 12-lead ECGs, and clinical laboratory evaluations will be eligible to participate in the study. All subjects must weigh between 60.0 to 100.0 kg, inclusive.

Women of childbearing potential must not be breastfeeding or pregnant and must be using an acceptable method of contraception. Women of childbearing potential must have a negative pregnancy test within 24 hours prior to dosing with study drug.

Study Drug: Includes investigational products (IP).

Study Drug for IM103349

Medication	Potency	IP/Non-IP
Process E Belatacept	250 mg/vial	IP
Process C Belatacept	250 mg/vial	IP

Abbreviation: IP = investigational product.

Study Assessments:

- Safety Outcome Measures: Safety assessments will be based on medical review of AE reports and the results of vital sign measurements, ECGs, physical examinations, and clinical laboratory tests. The incidence of observed AEs will be tabulated and reviewed for potential significance and clinical importance.
- Pharmacokinetic Measures: PK parameters (Cmax, time of maximum observed serum concentration [Tmax], AUC from time zero to the time of last quantifiable concentration [AUC(0-T)], AUC(INF), total body clearance (CLT), volume of distribution at steady state (Vss) and terminal half-life [T-HALF]) will be derived from serum concentration versus time data.
- Immunogenicity Measures: Immunogenicity determination will be based on antibody specificity for anti-belatacept antibodies and their corresponding titers in serum over time.

Statistical Considerations:

Sample Size: The PK of Process E belatacept and Process C belatacept will be considered equivalent if the 90% confidence intervals (CIs) for the ratios of geometric means (Process E belatacept relative to Process C belatacept) are contained within the equivalence interval 0.80 to 1.25 for both AUC(INF) and Cmax. If there is no difference in the PK of belatacept between the 2 manufacturing processes, then 67 subjects per treatment group will provide at least 99% and 99% power with respect to AUC(INF) and Cmax, respectively, to conclude equivalence between the 2 manufacturing processes. The overall power to conclude equivalence for both AUC(INF) and Cmax in this case is also at least 99%.

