If the PK of Process E belatacept is 11% greater or 10% less than the PK of Process C belatacept, then 67 subjects per treatment group will provide at least 96% and 84% power with respect to AUC(INF) and Cmax, respectively, to conclude equivalence between the 2 manufacturing processes. The overall power to conclude equivalence for both AUC(INF) and Cmax in this case is at least 81%.

These calculations assume that log(AUC[INF]) and log(Cmax) of belatacept are normally distributed with intersubject coefficients of variation no greater than 20% and 26%, respectively, based on the results of Study IM103024.

To allow for possible dropouts, an adequate number of subjects will need to meet the inclusion/exclusion criteria at screening so that a total of 176 subjects will be dosed including the originally planned 146 subjects (73 subjects per arm) and the 30 replacement subjects.

Endpoints: The primary endpoints are AUC(INF) and Cmax of belatacept. The secondary PK endpoints are Tmax, AUC(0-T), CLT, Vss, and T-HALF.

Safety endpoints include the occurrence of AEs, serious adverse events (SAEs), and AEs leading to discontinuation; results of clinical laboratory tests, vital sign measurements, ECG findings, and physical examinations; and marked abnormalities in clinical laboratory test results.

The immunogenicity endpoint includes the incidence of anti-belatacept antibodies.

Analyses:

The data from the 30 subjects who were enrolled and dosed at Site 2 will not be included in the primary analysis, and the data from the 30 replacement subjects to be dosed along with the data from the initial 116 subjects who were enrolled and dosed at the other sites will be used for the primary analysis. Details on handling of the data from the 30 subjects who were enrolled and dosed at Site 2 will be described in the statistical analysis plan.

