9.3 Clinical Study Report and Publications

For this single site protocol, the principal investigator for the site will sign the clinical study report.

The data collected during this study are confidential and proprietary to BMS. Any publications or abstracts arising from this study require approval by BMS prior to publication or presentation and must adhere to BMS's publication requirements as set forth in the approved clinical trial agreement (CTA). All draft publications, including abstracts or detailed summaries of any proposed presentations, must be submitted to BMS at the earliest practicable time for review, but

at any event not less than 30 days prior to submission or presentation unless otherwise set forth in the CTA. BMS shall have the right to delete any confidential or proprietary information contained in any proposed presentation or abstract and may delay publication for up to 60 days for purposes of filing a patent application.

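### The primary PK model leaves out clinic site although two clinics supply all the analysed data; the test stays valid, but a Site 1 versus Site 3 difference would cost precision that one model term recovers

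*Protocol*

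**What the plan says.** **Model.** Protocol 8.4.4, repeated in the Synopsis, states: "A linear fixed effect model with treatment as a fixed effect will be fitted to the log-transformed PK parameters". The parameters are AUC(INF), Cmax and AUC(0-T). SAP 7.1 and 7.7 describe the same model. Treatment is the only effect named in any of the four places.

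**Decision rule.** Equivalence is concluded if the 90% confidence intervals for the geometric mean ratios "are contained within the equivalence interval 0.80 to 1.25 for both AUC(INF) and Cmax" (Protocol Synopsis, Sample Size).

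**Clinics.** SAP section 1 reports that before Amendment 02 "146 subjects were dosed at 3 clinic sites: 60 at Site 1", with 30 more at Site 2 and 56 at Site 3. Site 2 is excluded from all summaries and analyses and appears in listings only. Its 30 subjects are replaced at Sites 1 and 3; the split between those two is not given. The 146 subjects intended for analysis (116 + 30) therefore all come from two clinics.

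**Randomisation.** SAP 2.2 assigns treatment "according to a computer-generated randomization scheme, stratified by weight categories". Protocol 4.4 gives the same four weight bands. Neither mentions site.

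**PK displays.** SAP 7.7 summarises PK by treatment and, optionally, by antibody status. No by-site display appears in the available text. The SAS code announced in SAP 7.7 is not shown, and table layouts are left to a separate Data Presentation Plan.

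**The concern.** Measured Cmax after a 30-minute infusion depends partly on local execution: how the infusion is prepared and run, and whether the end-of-infusion sample is drawn at the right moment. If Sites 1 and 3 differ systematically in measured Cmax or AUC, a treatment-only model counts that difference as unexplained subject-to-subject variation. The 90% CI becomes wider than it need be, and a pair of products that truly are equivalent becomes somewhat less likely to pass.

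Site is a recorded two-level baseline factor, so this loss can be avoided. As written, the plan also does not show whether the two clinics that carry the conclusion give similar ratios.

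**Working it through.** **Inputs**

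- Test: Protocol 8.4.4, "point estimates and the 2-sided 90% CIs for treatment differences on the log scale", that is, two one-sided 5% tests against ln 0.80 and ln 1.25 (±0.2231).
- True ratio: Protocol Synopsis, "If the PK of Process E belatacept is 11% greater or 10% less than the PK of Process C belatacept". I use 1.11.
- Variability: Protocol Synopsis, "intersubject coefficients of variation no greater than 20% and 26%, respectively, based on the results of Study IM103024" (AUC(INF) and Cmax in that order).
- n = 67 per arm; stated power at least 96% (AUC(INF)), 84% (Cmax) and 81% (both).
- Protocol 8.1 and SAP 5 are redacted, so the Synopsis is the source for the power statement.
- Assumed: ratio r between Sites 1 and 3 of 1.10, 1.15 or 1.20, with the two sites about equal in size. The documents give no value for r.

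**Step 1. Reproduce the plan's power.** Log SD = √ln(1+CV²), which is 0.198 for AUC(INF) and 0.2558 for Cmax.

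Hand check for Cmax: SE = 0.2558 × √(2/67) = 0.0442. The distance to the upper limit is ln 1.25 − ln 1.11 = 0.1188. Then 0.1188/0.0442 − 1.645 = 1.04, so power is about 85%.

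The t-based calculation, integrated over the sampling distribution of the variance, gives 96.5% (AUC(INF)) and 84.8% (Cmax). Their product is 81.8%. The stated figures are reproduced. At 58 per arm (116 subjects) the product is 75.3%, or 73.9% if the CV itself is used as the log SD, against about 74% in SAP section 1.

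**Step 2. Variance due to site.** With equal sites the between-site variance is (ln r)²/4. Site 1 must end with 60 to 90 of 146 subjects (41% to 62%), so the factor p(1−p) lies between 0.236 and 0.25, and the equal split is a close approximation. The Cmax log variance is ln(1 + 0.26²) = 0.0654.

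| r | (ln r)²/4 | relative to 0.0654 |
|---|---|---|
| 1.10 | 0.0023 | 3.5% |
| 1.15 | 0.0049 | 7.5% |
| 1.20 | 0.0083 | 12.7% |

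**Step 3. Cmax power at ratio 1.11, 67 per arm.** The documents do not say whether the 26% CV includes site variance, so both readings are shown. *Total CV:* the treatment-only SD is 0.2558, and adjusting reduces it to √(0.0654 − (ln r)²/4). *Within-site CV:* the adjusted SD is 0.2558, and omitting site raises it to √(0.0654 + (ln r)²/4). The adjusted model loses 1 of 132 degrees of freedom.

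| r | Total CV: treatment only | Total CV: with site | Within-site CV: treatment only | Within-site CV: with site |
|---|---|---|---|---|
| 1.00 | 84.8% | 84.8% | 84.8% | 84.8% |
| 1.10 | 84.8% | 85.9% | 83.8% | 84.8% |
| 1.15 | 84.8% | 87.2% | 82.5% | 84.8% |
| 1.20 | 84.8% | 88.8% | 80.9% | 84.8% |

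On the total reading, adjustment narrows the CI by 1.8%, 3.8% or 6.6%. On the within-site reading, omitting site raises the log-scale half-width from 0.0732 to 0.0745, 0.0759 or 0.0777.

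For AUC(INF) on the within-site reading, the treatment-only model falls from 96.5% to 95.7%, 94.7% or 93.2%. If both endpoints differed by site to the same degree, the products are 0.957 × 0.838 = 80%, 0.947 × 0.825 = 78% and 0.932 × 0.809 = 75%.

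**Step 4. Validity.** In 60,000 simulated trials per setting, with true Cmax ratio 1.25 and r up to 1.30, type I error was between 4.97% and 5.11%, with or without site in the model. Simulated power agreed with Step 3 to within half a point.

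**Step 5. What a by-site ratio can show.** With about 36 per arm per site (146/4 = 36.5), the SE of one site's log ratio is 0.2558 × √(2/36) = 0.060. The SE of the difference between two sites is 0.060 × √2 = 0.085. A 90% interval centred on no difference spans exp(±1.645 × 0.085), about 0.87 to 1.15.

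**The case against.** The other side has several good points.

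- **Site 2 is not evidence about Sites 1 and 3.** A reader might infer from the audit findings in SAP section 1 that conduct differs between the analysed clinics. Every documented deviation is at Site 2, which is excluded, and nothing in the documents describes a difference between the remaining two. This stands.
- **Chance imbalance is not a second harm.** A reader might infer that uneven site shares between arms bias the ratio. Without site blocking, the difference in Site 1 share between arms has SD about √(0.25 × 2/73) = 0.083, but the treatment-only CI already carries that variation, as Step 4 shows. This stands too.
- **The trial is not really written as single-site.** Protocol 9.3 says "For this single site protocol, the principal investigator for the site will sign the clinical study report", yet the Synopsis, 3.1 and 8.4 speak openly of Site 2 and other sites. The sentence is an editorial leftover with no statistical consequence.
- **There may be no shortfall against plan.** If the 26% is a total CV, the planned model keeps its stated power whatever the site difference. This is correct, and on that reading adjustment is purely a gain.
- **Procedures are standardised.** Protocol 4 fixes the pump type, filter and volume, and 5.5.1 moves the end-of-infusion sample if the infusion runs late. This makes a large site effect less likely but does not exclude one.
- **The model would change late.** At least 146 subjects had been dosed open-label before Amendment 02. The change therefore needs a documented reason, and the treatment-only result should still be reported.

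None of this removes the efficiency argument: adjustment helps on either CV reading if the sites differ, and costs almost nothing if they do not.

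**Conclusion.** The point holds as a matter of precision. Two clinics supply all the analysed data, and site is in neither the stratification nor any description of the model. With assumed site differences of 10% to 20% in Cmax, the stake is about 1 to 4 points of Cmax power at a true ratio of 1.11. It is a gain over plan if the 26% CV is total, and a loss against plan if the CV is within-site.

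These figures rest on an assumed site difference, roughly equal sites and 67 evaluable subjects per arm; the combined figures also treat the two endpoints as independent. The conclusion is also limited to the visible text, since the SAS code and the Data Presentation Plan could not be checked.

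The documents do not support saying that the equivalence test is invalid, that its type I error is inflated, or that the analysed clinics are known to differ. This is a cheap improvement worth making, not a defect that undermines the trial's conclusion.

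**What to change.** Before database lock:

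1. In Protocol 8.4.4 and SAP 7.1 and 7.7, prespecify clinic site (Site 1, Site 3) as a fixed effect alongside treatment in the model for log AUC(INF), Cmax and AUC(0-T).
2. Report the treatment-only model as a sensitivity analysis.
3. Tabulate geometric means and the Process E/C ratio by site, labelled descriptive. Step 5 shows that these cannot separate moderate disagreement from chance, so attach no test or criterion to them.
4. Record the reason for the change. Because the trial is open-label, also state that the choice was made without reference to PK results by treatment.
5. As an editorial point, correct the single-site wording in Protocol 9.3.

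The cost is one degree of freedom, some SAP and protocol wording, and a documented change to the primary model. No new data are needed.
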